### **13.11 Interim Analyses**

There will be no full interim analysis.

### **13.12 Other Evaluations**

#### **13.12.1 Pharmacokinetics**

Estimates of voclosporin exposure derived from this analysis will be examined for possible relationship to measures of efficacy and safety. Full details will be described in a separate analysis plan.

## **14. ETHICAL CONDUCT OF THE STUDY**

The study will be conducted according to the principles of the World Medical Association's Declaration of Helsinki [28] and the ICH guidelines for GCP [29]. Aurinia will ensure that the study complies with all local, federal, and country regulatory requirements.

The Investigator must ensure the confidentiality of all subjects participating in the study.

All anonymous data remains the property of Aurinia.

### **14.1 Informed Consent**

The ICF used for the study must comply with the Declaration of Helsinki, federal regulations, and ICH guidelines; and must have been approved by the IRB/EC/IEC prior to use. The Investigator or an authorized associate must explain the nature of the study and the treatment in such a manner that the subject is aware of potential benefits and risks. Subjects must also be informed that participation is voluntary and that they may withdraw from the study at any time, without prejudice. Subjects must be provided sufficient time to consider participation, including discussion with family members prior to signing the ICF. Documentation of the discussion and the date of informed consent must be recorded in the source documentation. After signing the ICF, subjects will be enrolled into the study and assigned a subject identification number that will be used on all subject documentation.

The informed consent can be signed up to 30 days before the screening Visit 1. If more than 30 days elapses between date of consent and the screening Visit 1, the subject should be asked to re-sign and date the consent form to confirm continued interest in study participation.

### **14.2 Institutional Review Board or EC/IEC**

The protocol, any protocol amendments and consent form for the proposed clinical study and any other documents required by the local IRB/EC/IEC must be submitted by the Investigator for review and approval to the IRB/EC/IEC. The Investigator must also ensure that the IRB/EC/IEC reviews the progress of the study on a regular basis and, if necessary, renews its approval of the study per local requirements.

## **15. QUALITY CONTROL AND QUALITY ASSURANCE**

The Investigator must ensure that all study-related site source data, study-related documents, and reports will be available, and that the provision of direct access for monitoring and auditing by Aurinia or its designees will be permitted. In addition, the Investigator must ensure that all study-related site source data, study-related documents, and reports will be made available for inspection by the appropriate Regulatory Authority and review by the IRB/EC/IEC.

The Investigator is responsible for notifying Aurinia in advance of an impending regulatory inspection. He/she may request that Aurinia provide support for preparation, if necessary. The Investigator is required to provide updates to Aurinia on the ongoing activities during the inspection, respond to any citations/objectionable findings (i.e., U.S. Food and Drug Administration Form 483) and to share any follow-up responses from the Regulatory Authority.

Accurate and reliable data collection will be assured by verification and cross-check of the eCRFs against the Investigator's records by the Study Monitor (source document verification). The Monitor will also review the Investigator's drug accountability records to ensure that the drug supplies are stored and dispensed appropriately. A comprehensive validation program will verify the data and queries will be generated for resolution by the Investigator. Throughout the study, Aurinia or its designates may review data as deemed necessary.

## **16. ADMINISTRATIVE PROCEDURES**

### **16.1 Sponsor's Responsibilities**

#### **16.1.1 Study Supplies**

Sites will be provided with all supplies required to manage this study. This will include but not be limited to the following:

- Investigator file(s) (for filing of all study-related documentation).
- Kits for collection, storage, and transportation of applicable samples required for central laboratories. These will also include all applicable guidelines and contact details.
- Contact list of all relevant study personnel.
- eCRF and completion guidelines (or equivalent electronic data capture system).
- Study reference manual.
- All study forms (e.g., SAE, pregnancy, drug accountability, etc.).

#### **16.1.2 Insurance**

Aurinia confirms that it carries liability insurance which protects non-employee physicians or Investigators/study staff against claims for which they may become liable as a result of damages caused by Aurinia products used in clinical studies. Insurance coverage is not extended to damages that the Investigators or third parties may suffer by reason of acts of commission or omission on the part of such Investigators or third parties and that are not in accordance with accepted common medical practices (*lege artis* procedures). Aurinia will reimburse the subject for all study-related injuries provided that the injury does not arise from the subject's misuse of the study treatment or failure to follow the Investigator's instructions.

#### **16.1.3 Study Monitoring**

The study will be monitored by representatives of Aurinia (or designee, which may include a contract research organization). If not monitored by Aurinia, documentation of delegation will be described in the Clinical Trial Agreement. It is understood that the responsible Monitor will contact and visit the Investigator regularly and will be allowed, on request, to inspect the various records of the study (eCRFs and other pertinent data) provided that subject confidentiality is maintained in accordance with local requirements.

It will be the Monitor's responsibility to inspect the eCRFs at regular intervals throughout the study (frequency outlined in a separate procedural document), to verify the adherence to the protocol and the completeness, consistency, and accuracy of the data being entered on them. The Monitor must have access to laboratory test reports and other subject records needed to

verify the entries on the eCRF. The Investigator (or his/her deputy) must agree to co-operate with the Monitor to ensure that any problems detected in the course of these monitoring visits are resolved.

## **16.2 Investigator's Responsibilities**

### **16.2.1 Reporting and Recording of Data**

All required study data must be entered in the eCRF created for the study. Training on the system will be provided to all sites, including instructions on how to address missing data, corrections, query procedures, and electronic signatures. Only individuals who are identified on the authorized signature page may enter/correct data in the eCRF. For those subjects who withdraw before completion of the study, all available efficacy and safety data must be entered in the eCRF. Incomplete or inconsistent data on the eCRF will result in data queries addressed to the Investigator for resolution.

### **16.2.2 Investigator Training**

All Investigators and their study personnel will receive training regarding the study procedures, study treatments, and GCP/regulations specific to the conduct of clinical studies. This training will take place prior to enrollment of the first subject at the study site, and must be documented and filed in the Investigator's Study Site File.

### **16.2.3 Source Documentation**

The Investigator must maintain adequate and accurate records to enable the conduct of the study to be fully documented and the study data to be subsequently verified.

Subject clinical source documents would include subject hospital/clinic records, physician's and nurse's notes, appointment book, original laboratory reports, ECG, X-ray, pathology and special assessment reports, signed ICFs, consultant letters, and subject screening and enrollment logs. These are to be separate and distinct from eCRFs. All data for the study must be available in source documentation, including oral and written communication with the subject regarding the study treatment (including the risks and benefits of the study). The date of informed consent must be recorded in the source documentation.

The Investigator must arrange for the retention of all study documentation (such as eCRFs, research files, and master files) for the duration specified in their respective site contract. The Investigator must keep these documents on file after completion or termination of the study according to local governing guidelines. Archived data may be held electronically, provided that a back-up copy exists and that a hard copy can be generated if required.

The Investigator must inform Aurinia immediately if any documents are lost, to be transferred to a different facility, or to be transferred to a different owner.

## **17. PROCEDURE FOR MODIFICATION OF PROTOCOL OR PREMATURE TERMINATION OF THE STUDY**

### **17.1 Protocol Waivers, Deviations and Violations**

Protocol waivers shall not be permitted.

The Investigator should not implement any deviation from, or changes of the protocol without written agreement from Aurinia and prior documented approval/favorable opinion from the IRB/IEC of an amendment, except where necessary to eliminate an immediate hazard(s) to study subjects, or when change(s) involves only logistical or administrative aspects of the study. If the Investigator must implement a deviation from, or a change of, the protocol to eliminate an immediate hazard(s) to study subjects without prior written approval, the implemented deviation or change and the reasons for it should be submitted in a timely manner to Aurinia and to the IRB/IEC as required by applicable local requirements.

The Investigator, or person designated by the Investigator, will document and record the preventative and/or corrective measures for any deviation from the approved protocol.

Accidental deviations from the protocol including violations of inclusion/exclusion criteria will be assessed as minor or major on a case-by-case basis. The criteria describing the deviation(s) and how they will be handled will be documented in the SAP.

Any amendment to the protocol requires written approval/favorable opinion by the IRB/IEC prior to its implementation, unless there are overriding safety reasons.

In some instances, an amendment may require a change to the ICF. The Investigator must receive an IRB/IEC approval/favorable opinion concerning the reviewed document prior to administering to study subjects.

### **17.2 Study Termination**

Aurinia reserves the right to terminate the study in its entirety or at a site at any time. Reasons for termination may include but are not limited to the following: unsatisfactory subject enrollment with respect to quality and/or quantity, site is unable to comply with the requirements of the protocol or GCP, or data recording is inaccurate and/or incomplete.

In terminating the study, Aurinia and the Investigator will assure that adequate consideration is given to the protection of the subjects. Both parties will arrange the procedures on an individual basis after review and consultation and in accordance with the study contract.

## **18. POLICY FOR PUBLICATION AND PRESENTATION OF DATA**

Aurinia is committed to the timely communication of data from clinical research trials, following the Pharmaceutical Research and Manufacturers of America principles [31]. Where possible, authorship will be agreed at the beginning of the study. The authors will form a publication committee and this committee will propose and develop appropriate scientific manuscripts or abstracts from the study data. Investigators may not present or publish partial or complete study results individually. Any manuscript or abstract proposed by the Investigators must be reviewed and approved in writing by Aurinia before submission for publication. Names of all Investigators participating in the study will be included in the publication.

The publication committee for a study will comprise of authors selected in adherence with the International Committee of Medical Journal Editors criteria [32] for authorship. If studies are multicenter, it may be appropriate to assign group authorship.

In addition, certain Aurinia employees involved in the design and conception of the protocol, study management and data analysis and interpretation are qualified authors and will be included in the publication committee.

## Appendix 1 Drug Therapy for the Treatment of Hypertension

Antihypertensive drug therapy for subjects who either have hypertension at screening or who develop hypertension while on study treatment may include the following:

- Dihydropyridine calcium channel blockers (e.g., amlodipine, nifedipine)
- Alpha-1-adrenergic blocking agents (e.g., doxazosin)
- Alpha-beta-blockers (e.g., carvedilol, labetalol)
- Thiazide diuretics (e.g., chlorthalidone or hydrochlorothiazide)

Excluded Drugs: While the ARBs and ACE inhibitors may also be effective in calcineurin inhibitor-associated hypertension, their dose adjustment or commencement is not permitted after the screening period (including stabilization visits) in this trial (see [Section 7.6.1, Prohibited Medications](#)).

### Recommended First and Second Line Therapies for Treatment of Hypertension

Titrate the following according to the timeframe given in the respective drug label:

First Line - select from one of the following:

- Amlodipine, 5 mg daily to achieve BP <140/90 mmHg; titrate to 10 mg daily if satisfactory results not obtained within 2 weeks
- Nifedipine XL, 30 mg daily; titrate to 60 mg and possibly 90 mg daily within 2 weeks
- 12.5 to 25 mg/day of chlorthalidone or hydrochlorothiazide

Second Line - may add from among the following to the first line therapy if a partial response is obtained:

- Labetalol, 100 mg BID; titrate to 200 mg BID, then 300 mg BID

Note: If the BP remains uncontrolled with the above-referenced maximum doses of first and second-line antihypertensive therapies, reduction of study treatment dose may be considered or it may be decided to discontinue study treatment and utilize antihypertensive therapies to achieve control of BP.

**If at any time, in the judgment of the treating physician in consultation with the Medical Monitor, the response to treatment is inadequate, the study treatment may be discontinued.**

## **Appendix 2 Measurement of Blood Pressure**

1. Whenever possible, BP measurements should be undertaken by the same study site personnel at each clinic visit.
2. Whenever possible, the BP determinations should be undertaken at approximately the same time of day for each study visit and at the same time in relations to prior study treatment ingestion.
3. The measurements should be undertaken prior to blood collection.
4. Prior to measuring BP, the study subject should be seated in a quiet room for at least 5 minutes, in a chair with his/her back supported and feet comfortably resting on the floor.
5. Due to the likelihood each arm can have a slightly different BP, it is strongly encouraged to use the same arm that was selected at screening for all measurements, supported at heart level.
6. No restrictive clothing should encircle the arm in which BP measurements are determined.
7. An appropriately sized cuff will be required wherein the cuff bladder encircles at least 80% of the upper portion of the arm.
8. Three serial BP readings will be undertaken with a minimum of 2 minutes between readings and with the cuff fully deflated between each determination.
9. The mean of the second and third of these 3 readings will be used as the study day BP value.
10. All measurements, along with the calculated mean value, will be recorded in the source documents. The mean of the second and third readings will be calculated within the EDC as the study day result.

### **Appendix 3 Classification of FSGS**

The epidemiology, classification and pathogenesis of FSGS has been reviewed by Reiser et al, 2017 [33].

According to this review, FSGS “is a histologic lesion, rather than a specific disease entity, that is commonly found to underlie the nephrotic syndrome in adults and children, particularly in the United States, Brazil, and many other countries. FSGS is characterized by the presence of sclerosis in parts (segmental) of some (focal) glomeruli on light microscopic examination of a kidney biopsy specimen.”

According to this review, FSGS can be classified into the following etiologies, based upon the known and/or postulated causes of this histologic pattern:

- “Primary or idiopathic FSGS, which most often presents with the nephrotic syndrome.”
- “Secondary FSGS, which most often presents with non-nephrotic proteinuria and, commonly, some degree of renal insufficiency. This category most commonly refers to FSGS that develops as an adaptive response to glomerular hypertrophy or hyperfiltration. This includes disorders associated with a reduced renal mass and/or renal vasodilation, such as unilateral renal agenesis. In addition, a nonspecific pattern of secondary FSGS can result from scarring produced by a previous injury (due to a variety of conditions, including active IgA nephropathy, vasculitis, and LN). Other secondary causes of FSGS include drugs and toxins (including heroin, interferon, and pamidronate) and viral infections (particularly HIV).”
- “Genetic causes of FSGS, which may present early in childhood with massive proteinuria and nephrotic syndrome or in adolescence or adulthood with less massive proteinuria.”

**Biopsy and diagnosis:** According to Reiser et al, “precise quantification of sclerotic glomeruli requires three-dimensional morphometric analysis of entire glomeruli and the examination of sufficient glomeruli to ensure that the biopsy specimen is representative of glomeruli in the whole kidney. Kidney biopsies with few glomeruli (i.e., fewer than 15) cannot confidently exclude the diagnosis of FSGS, and, due to sampling error, some cases will be misclassified as minimal change disease.”

“In patients who are found to have a FSGS lesion by light microscopy, the following approach can be used to distinguish between those with primary and secondary FSGS:

- Patients who present with nephrotic syndrome (ie, urine protein excretion >3.5 g/day and hypoalbuminemia), who exhibit extensive foot process effacement ( $\geq 80$  percent) on EM [electron microscopic] examination, and who have no identifiable risk factors associated with secondary FSGS (eg, viral infection, drugs) most likely have primary FSGS, although genetic forms of FSGS lesions cannot always be excluded with confidence. Thus, primary FSGS is always a diagnosis of exclusion.
- Patients who present with subnephrotic (ie, <3.5 g/day in an adult) or nephrotic-range proteinuria and a normal serum albumin concentration (ie, without nephrotic syndrome) and segmental foot process effacement (<80 percent) on EM [electron microscopic] examination most likely have secondary FSGS.”

#### Appendix 4 Conversion Table for Oral Corticosteroids

Compound	Equivalent Potency (mg)
Prednisone	5
Prednisolone	5
Cortisone	25
Hydrocortisone (cortisol)	20
Methylprednisolone	4
Triamcinolone	4
Dexamethasone	0.75

i.e.,

1 mg prednisone = 1 mg prednisolone

1 mg prednisone = 5 mg cortisone

1 mg prednisone = 4 mg hydrocortisone (cortisol)

1 mg prednisone = 0.8 mg methylprednisolone

1 mg prednisone = 0.8 mg triamcinolone

1 mg prednisone = 0.15 mg dexamethasone

## Appendix 5 Expanded List of Allowed Concomitant Medications

- Prophylactic therapy for steroid-induced bone loss (calcium with Vitamin D and/or a bisphosphonate).
- Low dose aspirin is allowed for cardiovascular prophylaxis.
- Minor GI AEs (such as nausea, vomiting and diarrhea) may be treated symptomatically (e.g., with loperamide for diarrhea or standard anti-emetics such as metoclopramide or domperidone for nausea and vomiting). Proton pump inhibitors or ranitidine are permitted for dyspepsia or gastric protection. Magnesium or aluminum containing antacids may be used, but should not be taken at the same time as study treatment; such antacids, if required, should be taken either 1 hour before or 2 hours after study treatment.
- Amphotericin or oral nystatin are permitted as infective prophylaxis against fungal infections, and low-dose sulfamethoxazole/trimethoprim is permitted as prophylaxis against *Pneumocystis carinii pneumonia*.
- Granulocyte colony stimulating factor is allowed to manage neutropenia in the presence of major infection (i.e., infections requiring IV antibiotics).
- Oral or IV iron preparations for iron deficiency and/or anemia.
- Erythropoietin is permitted for treatment of severe anemia (hemoglobin <10 mg/dL).
- Cytomegalovirus prophylaxis is permitted for example with oral valganciclovir.
- Acute intermittent administration of NSAIDs for not greater than 7 consecutive days is permitted.
- At the discretion of the Investigator, subjects with hyperlipidemia may be treated with lipid lowering agents (e.g., statins) in accordance with standard clinical practice. Doses must be stable in the 2 weeks prior to baseline.
- Subjects with nephrotic edema may be treated with diuretics during the screening period. Volume status should be optimized based on the clinical judgment of the Investigator and the doses of diuretics must be stable in the 2 weeks prior to baseline.
- ACEIs, ARBs, and aliskerin and other therapies are recommended, as per standard guidelines, but if used their dose must be stable throughout the study. Subjects receiving ACEIs or ARBs must be on a stable dose for at least 2 weeks prior to baseline.

- In the case of uncontrolled hypertension (systolic BP >165 mmHg or diastolic >105 mmHg on two successive measurements), the addition of a diuretic or calcium channel blocker only are permitted, together with dose decreases or interruption of study treatment per the instructions in [Section 7.7, Increased Blood Pressure](#).

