6. Stable proteinuria, renal function, and BP during the 2 weeks prior to baseline, as assessed by the Investigator. Changes in UPCR, eGFR, and/or BP during the screening period may be due to treatments administered (e.g., ACEIs and ARBs); and, therefore, may interfere with study assessments or outcomes, or may place the subject at increased risk. All subjects must be discussed with the medical monitor prior to initiation of study treatment.
7. Women of childbearing potential must have a negative serum pregnancy test prior to dispensing study treatment. Two effective forms of contraception must be used simultaneously unless abstinence is the chosen method. Subjects must use effective contraception during the study (see [Section 5.4, Adequate/Effective Contraception](#)).

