### 7.6.1 Prohibited Medications

The following medications cannot be taking during the study:

- Cytotoxic or other systemic immunosuppressants
- Initiation of new treatment or change in dosage of ARBs and/or ACE inhibitors within 2 weeks prior to baseline
- Vaccines using live organisms, viral or bacterial
- Current or planned use of ketoconazole or rifampin
- Concomitant use of other CYP3A4/5 inhibitors and inducers should be discussed with the Medical Monitor

[Appendix 6](#) contains a summary of additional treatment and food restrictions.

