### 7.6.2 Allowed Concomitant Medications

These medications are permitted during the study:

- Systemic corticosteroids as described in the Inclusion Criteria (see [Section 5.2, Inclusion Criteria](#)) and following the corticosteroid dosing guidelines (see [Section 7.1.2.2, Corticosteroids](#))
- Doses of ACEIs and/or ARBs as described in the Inclusion Criteria (see [Section 5.2, Inclusion Criteria](#))
- Doses of diuretics as described in the Inclusion Criteria (see [Section 5.2, Inclusion Criteria](#))
- Doses of statins as described in the Inclusion Criteria (see [Section 5.2, Inclusion Criteria](#))
- Topical steroids (e.g., nose, scalp, skin, inhaled)
- Herbal supplements can be used with caution and with approval by the Medical Monitor

Treatments which may be used as medically indicated, according to the judgment of the Investigator can be found in [Appendix 5](#). Treatments not included in this list may be acceptable in the study; such treatments should be verified with the Medical Monitor prior to use. A summary of treatment and food restrictions can be found in [Appendix 6](#).

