## Appendix 6 Summary of Treatment and Food Restrictions

Treatment	Washout Period	During Treatment	Reason
Immunosuppressants other than those allowed by protocol	30 days	Prohibited	Interferes with study efficacy endpoints
Aminoglycosides Amphotericin B Melphalan Ketoconazole Rifampin	14 days	Prohibited	May potentiate toxicity
NSAIDs chronic dosing (>7 consecutive days)	Prohibited	Prohibited	May potentiate nephrotoxicity
P-gp substrates	To be monitored	To be monitored	Drug-drug interaction
P-gp inhibitors	To be discussed with Medical Monitor	To be discussed with Medical Monitor	Drug-drug interaction
Androgenic steroids Cimetidine Fluconazole, itraconazole Macrolide antibiotics (azithromycin, clarithromycin, erythromycin) Metoclopramide Barbiturates and derivatives Carbamazepine Octreotide acetate Phenytoin Sulfadimidine (intravenous) Theophylline	To be discussed with Medical Monitor	To be discussed with Medical Monitor	Drugs interfering with voclosporin metabolism
ACEIs and ARBs	Stable dose for at least 2 weeks prior to baseline	Change or commencement prohibited	Interfere with primary endpoint assessment
Foods Grapefruit and grapefruit juice	24 hours	Prohibited	May affect the metabolism of voclosporin

Notes: ACEI = Angiotensin converting enzyme inhibitor; ARB = Angiotensin receptor blocker; NSAID = Non-steroidal anti-inflammatory drug; P-gp = P-glycoprotein.

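### Appendix 5 permits amphotericin as antifungal prophylaxis and Appendix 6 prohibits amphotericin B during treatment; neither states a route or form, and nothing says which list prevails

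*Combined protocol and SAP*

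**What the plan says.** Four places in the protocol bear on this.

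- **Appendix 5 (allowed medications):** "Amphotericin or oral nystatin are permitted as infective prophylaxis against fungal infections". The word for the oral route stands before nystatin only.
- **Appendix 6 (restrictions):** one row reads "Aminoglycosides Amphotericin B Melphalan Ketoconazole Rifampin". The row carries a 14-day washout and a prohibition during treatment, and the reason given is possible potentiation of toxicity. No route or form is attached to amphotericin B.
- **Section 7.6.2:** this gives Appendix 5 its force: "Treatments which may be used as medically indicated, according to the judgment of the Investigator can be found in" that appendix. It continues: "Treatments not included in this list may be acceptable in the study; such treatments should be verified with the Medical Monitor prior to use". Its last sentence then refers the reader to Appendix 6 for restrictions.
- **Section 7.6.1:** the list of prohibited medications includes "Current or planned use of ketoconazole or rifampin" but not amphotericin. It adds that Appendix 6 "contains a summary of additional treatment and food restrictions".

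**The concern.** Read as they stand, one list lets the Investigator use amphotericin on his or her own judgment and the other forbids it. Because the drug is on the Appendix 5 list, the Section 7.6.2 request to check unlisted treatments with the Medical Monitor does not apply to it. One site could use it in good faith while another withholds it.

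The stake is safety. The protocol gives toxicity as its own reason for the ban, and Section 1.2.4 names renal dysfunction as a known risk of calcineurin inhibitors, the class to which the study drug belongs. The question could plausibly arise in practice. Appendix 6 prohibits ketoconazole and asks that fluconazole and itraconazole be discussed with the Medical Monitor, so amphotericin and nystatin are the only antifungals that Appendix 5 offers.

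**Working it through.** No arithmetic applies. The check is whether anything in the text reconciles the two entries.

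| Feature | Appendix 5 | Appendix 6 |
|---|---|---|
| Name used | Amphotericin | Amphotericin B |
| Status | Permitted | Prohibited during treatment; 14-day washout |
| Use or reason | Antifungal prophylaxis | Toxicity |
| Route or form | None stated | None stated |

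1. **Route or form.** Both appendices state routes or limits for other drugs when they matter. Appendix 5 specifies oral nystatin, oral or IV iron and oral valganciclovir. Appendix 6 restricts the sulfadimidine entry to the intravenous route. NSAIDs appear on both lists and are reconciled by a limit in each: up to 7 consecutive days allowed, more than 7 prohibited. Amphotericin has no such qualifier in either place.

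2. **Name.** The only difference in naming is the letter B. Nothing in the protocol tells a site that this marks a different product or route.

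3. **Precedence.** Section 7.6.2 cites both appendices in the same paragraph and ranks neither. Section 7.6.1 treats Appendix 6 as adding to the prohibited list but does not say that it overrides Appendix 5. The absence of amphotericin from Section 7.6.1 is not itself a defect, because that section defers further restrictions to Appendix 6.

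4. **Other mentions.** Amphotericin appears nowhere else in the document, so no third passage decides the matter.

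5. **Safeguards already in place.** Under inclusion criterion 6 in Section 5.2, "All subjects must be discussed with the medical monitor prior to initiation of study treatment". Use at entry is therefore likely to be noticed, and the remaining exposure is mainly amphotericin started during the 24 weeks of treatment. Section 7.4.2 has central-laboratory creatinine and eGFR assessed at every visit, including unscheduled ones. Section 7.4.2.1 interrupts study drug when eGFR falls by more than 30% from baseline to below 90 mL/min/1.73 m², with a repeat within 48 hours. Section 7.6 requires all concomitant treatment to be recorded with dosage, dates and reason.

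6. **Limits of those safeguards.** Treatment visits fall at Weeks 2, 4, 8, 12, 18 and 24, so scheduled checks are up to 6 weeks apart (18 − 12 = 6; 24 − 18 = 6). Monitoring detects renal harm after the event and does not prevent it. The Appendix 6 row refers to toxicity in general, which eGFR covers only in part.

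**The case against.** The strongest reply is that the two entries describe different uses. Appendix 5 offers amphotericin as an alternative to oral nystatin, for prophylaxis only. Appendix 6 groups amphotericin B with aminoglycosides and melphalan under a washout, a setting that suggests systemic treatment. On that reading there is no clash. It is a reasonable guess at intent, and it stands as a possibility; but a site has to supply the distinction, because the protocol does not.

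A second reply is that a site reading Section 7.6.2 to its end reaches Appendix 6 and sees the ban. That is correct. A reader might infer that the prohibition is hidden from anyone relying on Section 7.6.2, and the text does not support that inference. What remains is that the site then has a permission and a prohibition with no rule for choosing between them.

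A third reply is that harm would be small and largely visible through routine renal monitoring. That lowers the severity but does not remove the ambiguity.

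A reader might also infer damage to the results. The documents do not support this either. Section 13.3.1 uses all enrolled subjects for the efficacy analyses. The per-protocol set only confirms the primary result, and it excludes subjects for major violations that are still to be defined in the SAP. Section 17.1 says that accidental deviations "will be assessed as minor or major on a case-by-case basis". Nothing indicates that a site acting on Appendix 5 would lose a subject from that set.

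**Conclusion.** The inconsistency is real and of low severity. The protocol gives two instructions on amphotericin that conflict as worded, and it contains nothing that reconciles them. A settled contradiction would be too strong a claim, since different forms may have been meant. Equally, the text does not establish that they were.

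Actual harm depends on two conditions: that the Appendix 6 ban was meant to cover the form a site would choose under Appendix 5, and that antifungal prophylaxis is needed during treatment. The documents give no frequency for the second, so the number of subjects affected cannot be estimated. The effect is confined to subject safety and uniform site conduct. No endpoint, analysis set or estimate changes.

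**What to change.** The sponsor should decide which form was intended and then make one of two edits.

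- **If no amphotericin is acceptable:** delete it from the Appendix 5 entry, so that only oral nystatin remains as permitted antifungal prophylaxis. This changes one line.
- **If only the systemic drug is barred:** write *Oral (non-absorbed) amphotericin or oral nystatin* in Appendix 5 and *Systemic amphotericin B* in Appendix 6. This changes two lines.

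Either edit can go into the next amendment, with a short note to sites in the meantime. There is no cost to design, visits, sample size or analysis.
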